13.2 Primary Efficacy Endpoint

The primary efficacy endpoint is:

- The change from baseline (assuming no treatment for severe hemophilia A) in FVIII activity, as measured by chromogenic substrate assay, at Week 52 (during Weeks 49 - 52) post-BMN 270 infusion

Each subject's FVIII activity level at Week 52 is defined as the median of the values obtained within the analysis window at Weeks 49-52 as defined in Appendix 20.1. The baseline value will be imputed as 1 IU/dL, since there will be no washout of severe hemophilia A subjects' usual FVIII prophylaxis (in order to avoid increasing the risk of bleeding) prior to BMN 270 infusion. Post-BMN 270 infusion values for FVIII activity will be excluded from analysis if obtained within 72 hours (or 3 calendar days if time is not available) since the last infusion of exogenous FVIII replacement therapy.

The change from baseline in the FVIII activity at Week 52 post-BMN 270 infusion will be tested using a one-sample t-test. The hypotheses are:

H_0 (null hypothesis): Change = 0 versus H_1 (alternative hypothesis): Change \neq 0.

Only positive changes indicate efficacy.

13.2.1 Primary Analysis for the Primary Efficacy Endpoint

The primary analysis of FVIII activity will be based on the mITT population. If any subject in the mITT population has no assessment available at Week 52, the imputation methods specified in Section 5.6 will be used to impute the missing value. Specifically, if the subject discontinues from the study prior to Week 52, the missing value will be imputed to be 0 IU/dL at Week 52; if the subject continues the study, the missing value will be imputed to be the smaller of the median value in the subject's last 4-week window prior to Week 52 containing a valid observation and the median value in the subject's next 4-week window post Week 52 containing a valid observation. If the value of the next 4-week window is unavailable (e.g., Week 52 is the last visit by the data cutoff date), the missing value will be imputed through linear extrapolation using the median values in last two 4-week windows prior to Week 52 containing a valid observation, capped at the value in the last 4-week window.

A listing of subjects with no assessment available at Week 52 will be provided, including the imputed value and associated analysis visit window as well as the next available FVIII activity value after Week 52 and associated analysis visit window, if available. This is to assess potential bias in missing data imputation.

13.2.2 Supportive and Sensitivity Analyses for the Primary Efficacy Endpoint

The FVIII activity level will be summarized descriptively in 4-week or 6-week analysis visit windows with missing data imputed from baseline up to the last possible visit by the data cutoff for the 1-year analysis. The visits and analysis visit windows are defined in Appendix 20.1 Analysis Visit Windows. Each subject's FVIII activity level in an analysis visit window is defined as the median of the values obtained within the window. The number and proportion of subjects achieving FVIII activity level per chromogenic assay of < LLoQ (3 IU/dL), between levels of \geq LLoQ (3 IU/dL) - < 5 IU/dL, between the levels of \geq 5 - < 15 IU/dL, between the levels of \geq 15 - < 40 IU/dL, between the levels of \geq 40 - \leq 150 IU/dL, and > 150 IU/dL will also be summarized every 4 or 6 weeks post-BMN 270 infusion up to data cutoff. The number and proportion of subjects whose FVIII activity is < 5, \geq 5 - < 40 and \geq 40 IU/dL will also be provided.

Boxplots of median FVIII activity values using chromogenic substrate assay by 4-week or 6-week windows (Appendix 20.1 Analysis Visit Windows) over time will be provided.

The 4-week or 6-week analysis will be repeated using efficacy evaluation period for supportive analysis of FVIII activity without imputation for the mITT population.

The maximum of each subject's FVIII activity levels (medians of the values in analysis visit windows defined in Appendix 20.1), and the time to the maximum level, will be summarized descriptively. The number and proportion of subjects whose maximum FVIII activity level is < LLoQ (3 IU/dL), between levels of \geq LLoQ (3 IU/dL) - < 5 IU/dL, between the levels of \geq 5 - < 15 IU/dL, between the levels of \geq 15 - < 40 IU/dL, between the levels of \geq 40 - \leq 150 IU/dL, and > 150 IU/dL will also be summarized.

The primary and supportive analyses described above may be conducted for FVIII activity levels measured by one-stage clotting assay.

To investigate the relationship between the FVIII activity values by one-stage clotting and chromogenic substrate assays, a linear regression to fit a line to the observed values by these two assays will be conducted for the mITT population.

The FVIII activity levels and their changes from baseline will be summarized descriptively at milestone timepoints defined as the end of every 6 months post-BMN 270 infusion (e.g., Week 26, Week 52 with the analysis visit windows defined in Appendix 20.1). Missing data will be imputed using the imputation methods specified in Section 5.6. In addition, proportion of subjects whose FVIII level is < LLoQ (3 IU/dL), between levels of \geq LLoQ (3 IU/dL) - < 5 IU/dL, between the levels of \geq 5 - < 15 IU/dL, between the levels of \geq 15 - < 40 IU/dL, between the levels of \geq 40 - \leq 150 IU/dL, and > 150 IU/dL will be

summarized. The change in FVIII activity between certain milestone timepoints (e.g., between Week 26 and Week 52) and between Week 52 and the maximal FVIII activity by Week 52 will also be summarized.

Exploratory analyses including univariate and multiple logistic regression may be performed to evaluate associations between demographic and baseline characteristics and other parameters and FVIII activity at Week 52 to assess potential predictors of variability.

One-sample t-test on the change from baseline in the FVIII activity at Week 52 using observed cases (i.e., no missing data imputation) will be performed as sensitivity analyses.

The primary analysis for the change from baseline in FVIII activity at Week 52 will be conducted for the PP population when applicable.

To investigate the robustness of the primary analysis, which uses the median FVIII activity value if more than one assessment falls within an analysis window, a sensitivity analysis may be performed using the mean of the multiple assessments. This sensitivity analysis will be based on the mITT population with the same imputation method as the primary analysis.

A mixed model for repeated measures (MMRM) approach may be used with the observed cases for the mITT population to evaluate the impact of missing data assuming missing at random. The model will include visit (every 4 weeks, from baseline to Week 52) as the only factor and will use an unstructured covariance matrix. The least squares (LS) mean change from baseline to Week 52 will be reported.

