5.6 Handling of Dropouts and Missing Data

If a subject withdraws from the study prematurely, the subject will be asked to complete an Early Termination Visit (ETV), the data from which will be included in summaries and analyses.

Missing dates or partially missing dates will be imputed conservatively for concomitant medications and adverse events (AEs) to ensure that an AE is considered treatment emergent when possible and the duration is the longest possible duration.

FVIII activity levels below the lower limit of quantitation (LLoQ) will be imputed as 0 IU/dL. To reduce variation caused by random fluctuation, FVIII activity will be analyzed as the median of observed values within each analysis visit window as defined in Appendix 20.1. Missing FVIII activity values will be imputed as follows.

- Dropout missing:
For subjects who discontinue from the study early, missing FVIII activity values post-discontinuation will be imputed to be 0 IU/dL through the data cutoff date for the analysis.
- Intermittent missing:
For subjects who continue the study, missing FVIII activity values (e.g., due to a missed study visit) will be imputed to be the smaller of the last prior non-missing value and the next non-missing value. In rare cases where the next value is unavailable for a subject who did not drop out, the missing value will be imputed through linear extrapolation using the last two prior non-missing values, capped at the last non-missing value.

Other missing data imputation for the primary efficacy endpoint and the secondary efficacy endpoints are specified in the corresponding analysis sections.

Other missing data will not be imputed unless otherwise stated.

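### The Week 26 to Week 52 change in FVIII activity is taken from imputed levels, so leavers add an artificial zero or an artificial total loss, depending on when they left

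*SAP*

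**What the plan says.** The current text is SAP version 2.0; version 1.0 has the same imputation rules.

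Section 13.2.2 summarises FVIII levels and changes from baseline at six-monthly milestones and states: "Missing data will be imputed using the imputation methods specified in Section 5.6". The same paragraph then adds "The change in FVIII activity between certain milestone timepoints (e.g., between Week 26 and Week 52"), and the change between Week 52 and the highest level reached by Week 52. Neither contrast is exempted from the imputation.

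Section 5.6 has three rules:

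- After dropout: "missing FVIII activity values post-discontinuation will be imputed to be 0 IU/dL through the data cutoff date for the analysis". Section 13.2.1 repeats this for the primary endpoint: "if the subject discontinues from the study prior to Week 52, the missing value will be imputed to be 0 IU/dL at Week 52".
- A gap in a continuing subject: the value "will be imputed to be the smaller of the last prior non-missing value and the next non-missing value".
- A gap with no later value: "linear extrapolation using the last two prior non-missing values, capped at the last non-missing value".

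Two analyses without imputation are planned in 13.2.2. One concerns levels by window: "The 4-week or 6-week analysis will be repeated using efficacy evaluation period for supportive analysis of FVIII activity without imputation for the mITT population". The other is a "One-sample t-test on the change from baseline in the FVIII activity at Week 52 using observed cases (i.e., no missing data imputation"). Neither is a within-subject change between milestones.

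**The concern.** Setting a missing level to 0, or to the smaller neighbour, can only lower that level. This is cautious when the quantity reported is the level itself or its change from a fixed baseline of 1 IU/dL. In a difference between two post-infusion levels, lowering the first term shrinks the fall and lowering the second enlarges it. The result then depends partly on when a subject left or missed samples, not on what happened to expression.

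The SAP does not label this contrast a durability measure, but readers are likely to use it as one. The 19-week corticosteroid regimen ends at Day 133 (Section 5.1), before the Week 26 window opens, so the contrast is the natural within-subject view of whether expression holds afterwards. An artificial 0 or an artificial total loss in a group of about 20 would be visible in the mean, and possibly in the standard deviation and range.

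**Working it through.** The SAP states no expected value for this contrast, so there is no figure of its own to reproduce.

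**Inputs from the SAP**

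- Week 26 window: Days 159 to 186, centre 172.5. Week 52 window: Days 341 to 368, centre 354.5. Centres 182 days apart (Appendix 20.1).
- Weeks 25-28 window: Days 173 to 200. Week 56 window: Days 369 to 406, centre 387.5 (Appendix 20.1).
- 22 subjects dosed (Section 4.5). The primary efficacy population is mITT, whose size is not given, so 22 is an upper limit.

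**Inputs assumed, not in the SAP:** the FVIII levels, the number and timing of leavers, and a linear decline.

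**Step 1. Section 5.6 applied to one subject (Week 52 minus Week 26)**

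- Leaves before any value in the Week 26 window: 0 - 0 = 0, read as no loss.
- Leaves after a Week 26 value x, before the Week 52 window: 0 - x = -x, read as total loss.
- Week 52 against the maximum M, either kind of leaver: 0 - M = -M. An early leaver is therefore unchanged in one contrast and a total loss in the other, though both stand in the same sentence.

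**Step 2. Effect on the mean**

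With e early leavers, l late leavers, Week 26 level x and fall d in the other subjects:

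mean change = [(22 - e - l)(-d) + l(-x) + e(0)] / 22

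For x = 60 and d = 15:

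- e = 1: 21(-15)/22 = -14.32
- e = 2: 20(-15)/22 = -13.64
- e = 3: 19(-15)/22 = -12.95
- l = 1: [21(-15) - 60]/22 = -17.05
- e = 3 and l = 1: [18(-15) - 60]/22 = -15.00

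One early leaver moves the mean by 15/22 = 0.68 IU/dL towards no change. One late leaver moves it by (60 - 15)/22 = 2.05 the other way. In the last case the two cancel exactly.

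Range over other assumed levels, with one leaver:

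| Week 26 to Week 52 | Without leavers | One early | One late |
|---|---|---|---|
| 20 to 15 | -5.00 | -4.77 | -5.68 |
| 30 to 25 | -5.00 | -4.77 | -6.14 |
| 40 to 20 | -20.00 | -19.09 | -20.91 |
| 60 to 45 | -15.00 | -14.32 | -17.05 |

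The early effect is always 1/22 = 4.5% of the fall. In these rows the late effect runs from 0.91/20 = 4.5% to 1.14/5 = 23%.

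**Step 3. Continuing subjects with a gap, linear decline**

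- Week 26 missing: the smaller neighbour is the later one. With nothing in Days 159 to 186, the next window holds only Days 187 to 200, centre 193.5. The starting level is taken 193.5 - 172.5 = 21 days late. 21/182 = 11.5% of that subject's fall is removed.
- Week 52 missing, Week 56 available: the smaller neighbour is Week 56. The end level is taken 387.5 - 354.5 = 33 days late. 33/182 = 18.1% is added to the fall.
- Week 52 missing with no later value: the capped extrapolation applies and forces neither a 0 nor a total loss.

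**The case against.** A reader might infer that the imputation makes early leavers look perfectly stable and so flatters durability overall. The documents do not support that. Only subjects who leave before a Week 26 value have both terms set to 0. Those who leave later count as total losses and, at the levels assumed in three of the four table rows, weigh more per subject (equally in the 40 to 20 row). The smaller-neighbour rule also works in both directions, and the error is larger when Week 52 is the missing value. With dropout numbers and timing unknown, no net direction can be claimed.

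The sponsor can add that the summary is descriptive, with no test or decision attached, and that much of the information appears elsewhere. Section 13.2.2 repeats the window levels without imputation. Section 13.2.1 lists every subject lacking a Week 52 assessment with the imputed value, expressly to check imputation bias. Section 7 summarises discontinuations before Week 52. All of that is true. But the repeat gives levels, not paired changes; the listing does not cover a missing Week 26; and the optional repeated-measures model reports change from baseline to Week 52.

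The strongest objection concerns the remedy. Zero after discontinuation is a deliberate failure rule. Restricting the contrast to subjects observed at both milestones would drop someone who left after losing expression; in the 60 to 45 example with one late leaver it moves -17.05 to -15.00. This stands, and it is why the observed-pair summary should be an addition, not a replacement.

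**Conclusion.** The point holds as a modest one. As written, the between-milestone change mixes observed changes with artificial zeros and artificial total losses, and no observed-pair version is planned. In the 60 to 45 illustration one leaver changes the mean fall by about 5% downwards or 14% upwards; a single gap in a continuing subject changes that subject's fall by about 12% downwards or 18% upwards. These figures rest on assumed levels, a linear decline and N = 22; with a smaller mITT population each leaver weighs more. If nobody is missing at either milestone the effect is nil. The primary test, the levels and the changes from baseline are not affected.

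**What to change.** In Section 13.2.2:

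- Also summarise the between-milestone change, and the Week 52 against maximum change, in subjects with observed, non-imputed window medians at both timepoints.
- Beside it, report how many discontinued before the first milestone and how many between the two.
- In the imputed version, do not count subjects set to 0 at both milestones as having a change of 0; show them only in the counts.
- Keep Section 5.6 imputation for levels and changes from baseline.

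The cost is a few sentences in the SAP and extra rows in one table. The downside is that the observed-pair summary describes only subjects who stayed; the counts and the retained imputed version keep that in view.

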4.5 Sample Size Determination

Approximately 20 subjects (22 actual) were planned to be dosed in the study, including at least 16 subjects who are AAV5 antibody-negative and up to 25% of the total number of subjects with an AAV5 antibody titer that is detectable but below the minimum required dilution (< 20) at Screening. For the primary efficacy endpoint, a sample size of 16 will provide 85% power to demonstrate that the change in human FVIII (hFVIII) activity at Week 52 (during Weeks 49 - 52) from baseline (baseline value imputed to be 1 IU/dL) is greater than 0, assuming an effect size of 0.8, using a one-sample t-test at the one-sided significance level of 0.025 (or equivalently, at the 2-sided significance level of 0.05).

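### Section 13.2.2 names logistic regression to find predictors of Week 52 FVIII activity, a continuous outcome, and ties no cut or ordinal grouping to the model

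*SAP*

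**What the plan says.** The predictor analysis is a single sentence in SAP Section 13.2.2: "Exploratory analyses including univariate and multiple logistic regression may be performed to evaluate associations between demographic and baseline characteristics". These are to be related, along with unspecified other parameters, to "FVIII activity at Week 52 to assess potential predictors of variability". The wording is the same in versions 1.0 and 2.0 of the SAP.

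The outcome is defined in Section 13.2: "Each subject's FVIII activity level at Week 52 is defined as the median of the values obtained within the analysis window at Weeks 49-52". It is measured in IU/dL and nothing there makes it categorical.

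Section 13.2.2 does list categories. One set has six levels, with boundaries at 3, 5, 15, 40 and 150 IU/dL. The other has three, introduced by "The number and proportion of subjects whose FVIII activity is < 5" and with a second boundary at 40. Both serve counts and proportions, and neither is linked to the logistic model. Linear regression appears in the same section for another purpose, comparing the two assays: "a linear regression to fit a line to the observed values by these two assays will be conducted".

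On numbers, Section 4.5 says: "Approximately 20 subjects (22 actual) were planned to be dosed in the study". Version 2.0 bases efficacy on the mITT population, a subset of those dosed whose size is not given. The predictor sentence names no population, covariate list or significance level.

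**The concern.** Logistic regression needs a binary or ordinal outcome, and the sentence supplies neither. An analyst must first decide how to split Week 52 FVIII activity, and the SAP offers several boundaries without choosing among them.

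If the split is binary, three things follow:

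- The parameter becomes the odds of exceeding one cut, not the level of activity whose variability is to be explained.
- Differences between subjects on the same side of the cut are discarded, which matters with so few subjects.
- The result depends on the cut. If the cut is picked after looking, the chance of a spurious predictor rises.

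A sparse group on one side of the cut also makes a model with several covariates unstable. What is at stake is how far the exploratory findings on between-subject variability in expression can be relied on.

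**Working it through.** **1. The SAP's own power figure.** The only one is for the primary test (Section 4.5): n = 16, effect size 0.8, one-sample t-test, one-sided 0.025. The noncentrality is 0.8 × √16 = 3.2 with 15 df, giving power 0.848. The stated 85% reproduces. No power is stated for the predictor analysis.

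**2. Inputs for the predictor analysis.**

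- From the SAP: N = 22 (the number dosed, so an upper limit for mITT); cuts of 5, 15 and 40 IU/dL (Section 13.2.2); values below the LLoQ of 3 IU/dL set to 0 (Sections 5.6 and 13.2.2).
- Assumed, because the SAP gives none: one normal predictor; log-normal activity with median 20 IU/dL and log-SD 1; true correlation with log activity of 0 or 0.5; two-sided 0.05.

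**3. Expected group sizes under these assumptions.**

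- Below 5 IU/dL: Φ(ln(5/20)) = Φ(−1.386) = 0.083; 22 × 0.083 = 1.8 subjects.
- At or above 40 IU/dL: 1 − Φ(ln(40/20)) = 1 − Φ(0.693) = 0.244; 22 × 0.244 = 5.4 subjects.

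Neither supports a logistic model with several covariates.

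**4. Simulated power at correlation 0.5, values below 3 set to 0.**

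| Analysis | Power |
|---|---|
| Linear regression on log(x+1) | about 66% |
| Proportional odds on the six SAP categories | about 67% |
| Binary logistic, likelihood-ratio test, across cuts | about 28–52% |
| Binary logistic, Wald test, across cuts | about 2–35% |

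The loss against linear regression is therefore 66 − 52 = 14 to 66 − 28 = 38 points with the likelihood-ratio test, and 66 − 35 = 31 to 66 − 2 = 64 points with the Wald test.

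**5. Dependence on correlation and balance.** A separate simulation used a normal outcome, N = 22 and correlations from 0.3 to 0.7. The share of linear-regression power kept was:

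| Subjects above the cut | Likelihood-ratio | Wald |
|---|---|---|
| 50% | 75–91% | 43–71% |
| 25% | 63–81% | 27–44% |
| 15% | 53–69% | 14–19% |

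With 15% above the cut, about 2–3% of data sets had no variation in the outcome and about 1–8% were completely separated.

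**6. Leaving the cut open.** With no association and likelihood-ratio tests at 5, 15 and 40 IU/dL, at least one reached p<0.05 in about 18% of trials, against 5% for linear regression. Part of the excess comes from the test itself, which rejects in about 6–8% at a single cut at this sample size. The rest comes from having three cuts to choose from. When the association was real (correlation 0.5, same distribution without the zeros), the three cuts disagreed on significance in 64% of trials.

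**The case against.** The strongest reply is that little is fixed here. The sentence calls the analysis exploratory, says it may be performed, and introduces logistic regression with a word that leaves room for other models. No claim or significance level rests on it. A reader might infer that the SAP commits to testing predictors by logistic regression and will usually miss real ones. The text does not support that, because linear models are not excluded.

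A reader might also infer that logistic regression loses most of the power at this sample size. That is not a general result. It holds for Wald tests at unbalanced cuts, and for the likelihood-ratio test at an extreme cut such as 5 IU/dL (28/66, or 42% of linear power kept). At cuts nearer the middle of the distribution the likelihood-ratio test keeps most of it. The SAP specifies neither test nor cut.

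Nor is a binary split the only reading. The paragraph just before the logistic sentence sorts FVIII levels into six ordered categories, and a proportional-odds model on these loses almost nothing. The null hypotheses are also less different than they may seem: if predictor and outcome are independent, both hold, and what differs is the parameter estimated.

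Finally, a log-normal outcome favours a log-scale linear model, and the zeros assigned to dropouts under Section 5.6 were not simulated.

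All of this limits the size of the point. It does not remove it. The only method named for the predictor question does not fit the outcome named in the same sentence, and the ordinal reading is as unspecified as the binary one.

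**Conclusion.** The point holds as a minor one. Section 13.2.2 pairs logistic regression with a continuous outcome and supplies neither a cut nor an ordinal grouping. Under the assumed distribution and a correlation of 0.5, a binary model would have about 28–52% power (likelihood-ratio) or 2–35% (Wald), against about 66% for linear regression on log(x+1). An open choice among three of the SAP's cuts gives roughly an 18% chance of at least one nominally significant result when there is no association.

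These figures rest on an assumed median, spread and correlation and on N = 22; the mITT population may be smaller. The direction is firmer than the size: binary splitting lost power at every cut, test and non-zero correlation tried, but the amount varied widely. The primary t-test and its 85% power statement are untouched.

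**What to change.** In Section 13.2.2, name linear regression of Week 52 FVIII activity on a log(x+1) scale as the main exploratory predictor analysis. The added 1 accommodates values below the LLoQ, which are set to 0. Limit the model to few covariates and report coefficients with 95% CIs. A proportional-odds model on the six categories already listed is an acceptable alternative if stated in advance. Keep any binary logistic model as a secondary analysis only, at one cut fixed beforehand.

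The cost is about one sentence of SAP text and no new data. Coefficients on a log scale are slightly harder to communicate than odds of reaching a familiar threshold.
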